4.10 PROCEDURES FOR MAINTAINING AND BREAKING RANDOMIZATION CODES

Each type of test article except for the subject's habitual spectacles is assigned and labeled with a unique lens ID code (also serves as the randomization code). The identity of the control lens type (Oasys) will be masked to subjects.

The test article mask shall not be broken unless information concerning the lens type is necessary for the urgent medical treatment of a subject. The Sponsor should be notified before the mask is broken.

When dispensing test articles, the following steps should be followed to maintain randomization codes:

1. The designee (documented on the delegation log) will consult the randomization scheme to obtain the study test article assignment for that subject prior to dispensing.

2. The designee will record the subject's number on the appropriate line of the randomization scheme.

The designee will pull the appropriate test articles from the study supply. All test articles that were opened, whether dispensed or not, must be recorded on the Test Article Accountability Log in the "Dispensed" section.

4.11 REPORTING PRODUCT QUALITY COMPLAINTS

A Product Quality Complaint (PQC) refers to any written, electronic, or oral communication that alleges deficiencies related to the identity, quality, durability, reliability, safety, effectiveness or performance of test articles after they have been released for clinical trial use. A PQC is associated with any investigational product (i.e. product manufactured or supplied specifically for a clinical trial).

Complaint Handling

Once site personnel have become aware that a PQC has occurred, it shall then be recorded in the EDC system, which triggers an automatic email notification to the appropriate COM/CRA and Clinical QA representative. In cases where the EDC system in use is not configured to send automatic notifications, then the COM/CRA is responsible for notifying Clinical QA upon discovery that a PQC has occurred.

Upon receipt of the EDC notification the COM/CRA shall complete the applicable sections of the [REDACTED] or electronic equivalent).

For each complaint, the following minimum information shall be recorded by the CRA/COM on the [REDACTED]:

- Date the complaint was received/recorded in the EDC System (Date of Sponsor Awareness)
- Who received the complaint
- Study number
- Investigational site information (contact name, site ID, telephone number)
- Lot number(s)
- Unique Subject Identifier(s)
- Indication of who first observed complaint (site personnel or subject)
- OD/OS indication, along with whether or not the lens was inserted
- Any related AE number if applicable
- Detailed complaint description (scheduled/unscheduled visit, wear time, symptoms, resolution of symptoms, etc.)
- Eye Care Provider objective (slit lamp) findings if applicable
- Confirmation of product availability for return (and tracking information, if available), or rationale if product is not available for return (Refer to [REDACTED] for test article return instructions)

Clinical QA will assign a unique number to the PQC. Complaint numbering is assigned as follows:

5.1 WITHDRAWAL CRITERIA

A subject may be withdrawn from the study for any of the following reasons:

- Lost to follow-up
- Withdrawal of consent
- Death

- Subject was randomized but did not satisfactorily complete the fitting process,
- A scheduled visit is missed,
- Subject no longer met eligibility criteria (i.e. subject became pregnant during the study),
- Discontinuation of study treatment as a result of the investigator's belief that for safety reasons (e.g., adverse event) it is in the best interest of the subject to stop treatment.
- Non-compliance to the protocol.

For discontinued subjects, the Investigator will:

- Update the enrollment log to document reason for discontinuation and provide to CRA
- Complete the "last" Follow-up Visit form (scheduled or unscheduled)
- Complete the Final Evaluation form, indicating the reason that the subject was discontinued from the study
- Record the spherocylindrical refraction with best corrected distance visual acuity
- Collect used study lenses and test articles (worn or brought to the visit) from the subject and discard them
- Collect all unused study lenses and test articles from the subject

Subjects becoming pregnant during the study will be discontinued. Once discontinued, pregnant participants and their fetuses will not be monitored for study related purposes. At the Investigators' discretion, the study participant may be followed by the Investigator through delivery. However, this data will not be collected as part of the clinical study database. Pregnant participants are not discontinued from contact lens or solution related studies for safety concerns, but due to general concerns relating to pregnancy and contact lens use. Specifically, pregnant women are discontinued due to fluctuations in refractive error and/or visual acuity that occur secondary to systemic hormonal changes, and not due to unforeseen health risks to the mother or fetus.

Investigators may be asked to replace discontinued subjects if the minimum target number of total subjects across all sites may otherwise not be met.

In cases where a subject is lost to follow-up, every possible effort must be made to contact the subject and determine the reason for discontinuation / withdrawal. The measures taken to follow up must be documented including two written attempts and a certified letter as the final attempt.

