4.1 PRIMARY AND SECONDARY ENDPOINTS

4.1.1 Primary Efficacy and Safety Endpoints:

The co-primary endpoints for efficacy evaluations are:

1. Eyestrain caused by glare score. This will be assessed using eyestrain patient reported outcomes.
2. Monocular distance visual acuity on LogMAR scale using ETDRS charts.

The primary endpoint for safety evaluation is physiological findings (grade 3 or higher) using slit lamp. The measures include edema, corneal neovascularization, corneal staining, conjunctival injection, tarsal abnormalities, and other complications using the FDA slit lamp grading scale 0 to 4, where 0 = none, 1 = trace, 2 = Mild, 3 = moderate and 4 = severe.

4.1.2 Secondary Efficacy and Safety Endpoints:

The secondary endpoints are average daily wear time (in hours) and presence of ocular symptom (yes/no).

Both primary and secondary endpoints will be evaluated at each follow-up visit.

The subject's adverse events, keratometry changes, lens deposit, reasons for discontinuation, lens damage, number and reasons for unscheduled lens replacement, overall comfort, overall vision and overall handling will be monitored at the follow-up visits.

4.1.3 Primary Hypotheses:

1. Efficacy (Eyestrain caused by glare): Subjects wearing the JVICI Investigational Test contact lenses on a daily wear basis report eyestrain caused by glare that is, on average, significantly lower to that of subjects wearing ACUVUE® OASYS® contact lenses on a daily wear basis. The assessments will be made at the 2-, 4-, 8- and 12-week follow-up visits.
2. Efficacy (Visual Acuity): Subjects wearing the JVICI Investigational Test contact lenses on a daily wear basis report an average distance monocular logMAR visual acuity that is statistically no different to that of subjects wearing ACUVUE® OASYS® contact lenses on a daily wear basis. The assessments will be made at the 2-, 4-, 8- and 12-week follow-up visits.
3. Safety (Slit Lamp Findings): Subjects wearing the JVICI Investigational Test contact lenses on a daily wear basis have a percentage of grade 3 or higher slit lamp findings that is statistically no different to that of

subjects wearing ACUVUE® OASYS® Contact Lenses on a daily wear basis. The assessments will be made at each follow-up visit.

4.1.4 Secondary Hypotheses:

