4.2 INCLUSION CRITERIA

Potential subjects must satisfy all of the following criteria to be enrolled in the study:

Subjects should meet all study Inclusion Criteria as outlined below:

1. The subject must read and sign the Informed Consent form.
2. The subject must appear able and willing to adhere to the instructions set forth in this clinical protocol.
3. Healthy adult males or females age ≥ 18 years of age with signed informed consent. Eligible presbyopes will be those that wear full distance contact lenses in both eyes, then wear reading glasses over them.
4. The subject's optimal vertexed spherical equivalent distance correction must be between -1.00 and -6.00D.
5. The subject's refractive cylinder must be ≤ 1.00 D in each eye.
6. The subject must have visual acuity best correctable to 20/25+3 or better for each eye.
7. Subjects should own a wearable pair of spectacles.
8. The subject is a current spherical soft contact lens wearer (defined as a minimum of 6 hours of DW per day, at least 5 days per week, for a minimum of 1 month prior to the study) and willing to wear the study lenses on a similar basis.
9. Subjects must be able and willing to wear the study lenses at least 6 hours a day, a minimum of 5 days per week
10. The subject must have normal eyes (i.e., no ocular medications or infections of any type).

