1	
Concomitant Medications and Medical History Review
 
Record the concomitant medications and review the subject's medical history, specifically noting any changes from baseline.
	
2	
Wearing Time
 
Record the average wearing time and comfortable wearing time.
	
3	
Compliance
 
Confirm compliance with the prescribed wear schedule, including adherence to the rub regime.
	
4	
Use of Lens Rewetting Drops
 
The subjects will record the approximate daily use of lens rewetting drops (i.e., how many times per day on average).
	
5	
Subject-reported Ocular Symptoms
 
The subject will respond to a Symptoms Questionnaire.
	

VISIT 2: 7-DAY FOLLOW-UP

(Follow-up #1, 6-8 days after Visit 1)

The following information will be collected:

Steps		Details	
6	Glare Questionnaire	The subject will respond to the Eyestrain Caused by Glare Questionnaire in regards to their study lenses.	
7	Project-Specific Questionnaire	The subject will respond to the Project-Specific Questionnaire	
8	CLUE Follow-up Questionnaire	The subject will respond to the CLUE Follow-up Questionnaire	
9	Patient Reported Outcomes	
Subjects will respond to the following individual questions.
 
 1. Subjective Comfort (Item ID: ISOC0001) 2. Subjective Vision (Item ID: ISOV0001) 3. Subjective Handling (Item ID: ISOH0001) 	
10	Lens Preferences	Subjects will respond to preference questions relating back to their habitual lenses.	
11	GSI Product Performance Questionnaire	Subjects will respond to the GSI Product Performance Questionnaire.	
12	Entrance Visual Acuity	Record the distance visual acuity with the study contact lenses (OD, OS, and OU) to the nearest letter. Smaller lines must be shown until the subject incorrectly identifies at least 50% of the letters.	
13	Spherical Over-refraction	Perform a spherical over-refraction OD and OS using any acceptable means (i.e., phoropter, trial lenses, flipper bars) in normal room illumination and record the resultant distance Snellen visual acuity OD and OS.	
14	Lens Fit Assessment:	
Subjective Assessment of the Lens Fit. If the fit is graded as unacceptable based on the criteria below, then the subject is discontinued from the study and will not be replaced.
 
 1. Limbal exposure in any gaze 2. Edge lift 3. Insufficient and/or excessive movement in all three movement categories 	

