2.2. Analysis Sets

2.2.1. Efficacy Analysis Set

Efficacy analyses will be performed on all randomized subjects who completed the study and did not substantially deviate from the protocol as determined by the trial cohort review committee prior to database hard lock (Per-protocol population). Justification of excluding subjects with protocol deviations in the analysis population will be documented in a memo to file. Additional post-hoc analyses may be conducted by including all randomized subjects who have been successfully dispensed and have at least one follow-up visit (i.e. all available data).

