4.2. Disposition Information

The disposition (accountability) of all enrolled subjects will be presented by study lens and overall to show the number and percentage of subjects in each of the following status subgroups:

1. Completed (Phase I): Subjects are considered to have completed Phase I of the study if they have completed all scheduled visits through Visit 6 (12-week Follow-up Visit).
2. Discontinued: Subjects are considered to have discontinued from the study if they are (i) randomized (ii) Successfully Dispensed and (iii) discontinued because of one of the following reasons: Unsatisfactory Lens Fitting due to study lens (a) Withdrew Consent (b) Lost to Follow Up (c) Subject no longer meets eligibility criteria (e.g. pregnancy) (d) Subject withdrawn by PI due to non-compliance to protocol (e) Discontinuation of study treatment as a result of the investigator's belief that for safety (f) Reasons it is in the best interest of the subject to stop treatment (g) Study lens no longer available (h) A scheduled visit was missed.
3. Total dispensed: Completed + Discontinued
4. Enrolled not Successfully Dispensed: Subjects are considered to be Enrolled Not Successfully Dispensed Subjects if they were (i) enrolled to the study (provided informed consent) but failed to satisfy the eligibility criteria (inclusion/exclusion criteria), (ii) were not randomized to study lens for any reason or (iii) if they are randomized but did not satisfactorily complete the dispensing process. This includes subjects who were dispensed a different type of study lens for each eye or who were dispensed same study lens for both eyes but did not return for any follow-up visits.
5. Total enrolled: Completed + Discontinued + Enrolled not Successfully Dispensed

The percentage will be calculated using total enrolled as denominator.

Safety and efficacy analysis sets will be defined as subsets of dispensed subjects (Completed + Discontinued).

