4.3. Treatment Compliance

Summaries of subjects' compliance information will be reported through tables for wear time and comfortable wear time.

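### Wear time can help decide who stays in the wear-time analysis, because low wear may lead to withdrawal and the efficacy set keeps only completers

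*Protocol*

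**What the plan says.** **The schedule.** Inclusion criterion 9 (Protocol 4.2) reads: "Subjects must be able and willing to wear the study lenses at least 6 hours a day, a minimum of 5 days per week". Protocol 4.4 repeats this as advice to subjects.

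**The check.** At each follow-up visit, Protocol 4.7.1 asks the site to "Confirm compliance with the prescribed wear schedule, including adherence to the rub regime". In SAP 4.3, "compliance information will be reported through tables for wear time and comfortable wear time".

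**The consequence.** Protocol 5.1 opens with "A subject may be withdrawn from the study for any of the following reasons", and the list includes "Non-compliance to the protocol". SAP 4.2 has the matching discontinuation reason: "Subject withdrawn by PI due to non-compliance to protocol". Neither document says how much missed wear counts as non-compliance.

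**The analysis set.** SAP 2.2.1 limits efficacy analyses to randomised subjects "who completed the study and did not substantially deviate from the protocol as determined by the trial cohort review committee". An analysis of all successfully dispensed subjects with at least one follow-up visit is mentioned there, but only as an optional post hoc addition.

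**The endpoint.** Average daily wear time in hours is the secondary efficacy endpoint (Protocol 4.1.2, SAP 5.2.1). The hypothesis is that the lenses do not differ statistically, and no margin is given (Protocol 4.1.4, SAP 1.4.2).

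**The concern.** Read together, these sections let the value of the endpoint influence whether a subject is counted. Someone who wears the assigned lens for fewer hours than prescribed is showing what the wear-time endpoint is meant to detect. The same report of hours can count as non-compliance and lead to withdrawal. Once withdrawn, the subject is not a completer, and the whole record leaves the comparison, including visits already made.

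The form of the hypothesis adds to the problem. The hoped-for result is a non-significant difference with no margin, so anything that shrinks a true deficit on Test, or reduces the number analysed, makes that result easier to obtain. Withdrawal is also discretionary. SAP 1.6 says the variable shade of the Test lens rules out full masking, so removal could differ between arms.

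**Working it through.** **1. The plan's own figure.** The only design number for wear time is the Bonferroni level in SAP 5.2.2: 0.05/4 = 0.0125, with 98.75% intervals. It reproduces exactly. (Protocol 9.1 uses 0.05/5 = 0.01 over five visits, but SAP 1.1 says the SAP supersedes Protocol section 9.) No mean, SD, effect size or power is stated for wear time, so every wear-time value below is an assumption.

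**2. Limiting case: everyone below 6 h is removed in both arms.** For a normal distribution cut from below at c, the remaining mean is μ + σ·φ(a)/[1 − Φ(a)], with a = (c − μ)/σ.

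- Control, mean 12 and SD 3: a = −2, remaining mean 12.17 h.
- Test, mean 11 and SD 3: a = −1.67, remaining mean 11.31 h.
- Visible difference: 0.85 h against a true 1.0 h.

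| Control mean, SD (h) | Visible difference for a true 1 h loss |
|---|---|
| 10, 3 | 0.68 h |
| 12, 3 | 0.85 h |
| 12, 2 | 0.97 h |
| 13, 2 | 0.99 h |

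Over a wider grid (Control mean 8 to 14 h, SD 2 to 4 h, true loss 1 or 2 h), 42% to 100% of the true difference remained. Attenuation is heavy only when wear times lie close to 6 h.

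**3. Effect on the test.** Take 50 per arm and two-sided α = 0.0125. Power on the full set is Φ(d/√(2σ²/n) − 2.50). With d = 1 and σ = 3, the standard error is 0.6 and power is 20%. After removal at Control mean 12 h it is 16%, and at mean 10 h it is 11%. With σ = 2 and mean 12 h it goes from 50% to 49%.

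**4. An intolerant subgroup.** Suppose 10% of Test subjects manage 4 h and everyone else is at 12 h.

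- None removed: loss = 0.10 × 8 = 0.8 h.
- Half of them removed: (0.05/0.95) × 8 = 0.42 h.
- All removed: 0 h.

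A simulation (4,000 runs per setting; others at mean 13 h, SD 2; 10% of Test at about 4.5 h) gave differences of 0.86, 0.46 and about 0 h. The rejection rates at 0.0125 were 16%, 5% and 1%.

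**5. Direction.** With equal means of 12 h, Control SD 2 and Test SD 3, removal below 6 h leaves Test apparently 0.16 h higher. With Test SD 4 the figure is 0.55 h. With identical distributions there is no bias.

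**6. Would the missing-data provision catch it?** SAP 5.1.2 adds multiple imputation only when dropout exceeds 15%. Six of 60 Test subjects withdrawn for low wear is 10% of that arm but 6/120 = 5% of all subjects, so this alone would not trigger it.

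**The case against.** A reader might infer that wear time **is** biased, that the distribution is cut at 6 h in both arms, and that the error always favours no difference. The documents do not support any of these.

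- Withdrawal is permissive and no threshold is set. A clean cut at 6 h is a limiting case.
- Compliance is more than hours: days per week and the rub regime also count. SAP 4.3 only specifies tables and triggers no exclusion.
- SAP section 3 defines a protocol deviation as something under the investigator's control. A subject's intolerance of a lens hardly fits, which weakens the route through substantial deviation. Exclusions are also decided before hard lock and documented.
- The direction depends on how the low tails differ between arms, as step 5 shows.

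There are also safeguards and limits on the size. Protocol 9.1 calls for summaries separately for completed and discontinued subjects. SAP 4.2 and 4.6 report disposition by lens and reasons with lens type. Entrants already wear lenses at least 6 h a day (criterion 8), so few may fall below. In the SAP's three historical studies, 4 + 2 + 6 = 12 of 263 dispensed subjects (4.6%) discontinued for any reason, though wear periods there were shorter.

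All of this stands and limits how strongly the point can be put. It does not remove the point. Descriptive tables would show that low wearers had left, but the t-test would still be computed without them. Discretion without a threshold makes the selection unpredictable; it does not prevent it. The remedy in SAP 2.2.1 is optional and post hoc.

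**Conclusion.** The concern holds in a limited form. Inclusion in the wear-time comparison can depend on wear time itself, mainly through discretionary withdrawal followed by the completer-only efficacy set. If Test lowers wear, the likely effect is to shrink the difference toward the hypothesised result. Unequal spread, or removal that differs by arm, could push it the other way.

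The size cannot be derived from the documents. Under the assumptions of step 2, a true 1 h loss shows as 0.68 to 0.99 h. It can vanish if the loss is concentrated in a small subgroup that is entirely withdrawn, and it is untouched if nobody is withdrawn for low wear. The endpoint is secondary and all hypotheses are declared exploratory (Protocol 3.1, SAP 1.4), so this is a modest weakness that is worth closing because it costs little.

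A reader might also conclude that Protocol 5.1 needs rewording. It does not. The bias arises when recorded data are discarded at analysis, and that can be put right in the SAP.

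**What to change.** Change the SAP only:

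1. In 2.2.1 and 5.2.2, pre-specify the wear-time analysis on all successfully dispensed subjects, using every recorded visit of the 12-week study-lens period, including visits of subjects later withdrawn. Wear time is also recorded at the 1-week visit, which the SAP's wear-time model leaves out. Include that visit in the model so that a subject withdrawn then still contributes, and keep the four comparisons and the 0.0125 level.
2. State that, for this endpoint, low reported wear is an outcome and not a substantial deviation.
3. Report withdrawals for low wear by arm, separately from other non-compliance, which SAP 4.2 groups under one reason.

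The planned mixed model already handles incomplete records, so keeping the earlier low values lets it use the information that led to withdrawal.

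The cost is a few sentences and one extra line in a table, with no new data collection. The small downside is that wear time is analysed on a different set from eyestrain and acuity. Protocol 5.1 stays as it is, and this point asks for no change to the efficacy set for those two endpoints.

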6.1 PRESTUDY AND CONCOMITANT THERAPY

Concomitant medications will be documented during screening and during the study. Disallowed medications for this study include those medications new to the subject within the past month and pose a threat to safe and comfortable contact lens wear.

6.2 MONITORING TREATMENT COMPLIANCE

Johnson & Johnson Vision Care, Inc. representatives or designees will monitor the study in a manner consistent with ICH GCP E6. The study monitors will maintain close contact with the Principal Investigator and the Investigator's designated staff. The monitor's responsibilities will include:

- Ensuring that the investigation is being conducted according to the protocol
- Ensuring the rights and wellbeing of subjects are protected
- Ensuring that protocol deviations are documented with corrective action plans, as applicable
- Ensuring that the site has sufficient test article and supplies
- Clarifying questions regarding the study
- Resolving study issues or problems that may arise
- Reviewing the study records to ensure completeness and accuracy
- Study and subject source document records reviewed will include:

- The Information and Consent Form per 21CFR Parts 50 and 56 and the HIPAA documents
- Source documentation including consenting and HIPAA process, medical history, concomitant medications, and adverse event information as applicable. The source document should be initialed and dated by the study investigator/s.
- Investigational product shipping, dispensing, accountability, and return/destruction records
- Study related Regulatory documents as per ICH E3 section 8

A separate monitoring plan will be provided.

